12.1 Definitions

An adverse event can occur on any clinical trial; it is the responsibility of the Principal Investigator and his/her research team to identify, review and report all necessary adverse events to the institutional IRB, the sponsor and governmental agencies (i.e., NCI and/or FDA) as appropriate. Adverse events should be identified through standard, routine protocol review and clinical assessment of each subject participating in the clinical trial. This review should be timely in order to meet the requirements for adverse event reporting defined below.

An adverse event An Adverse Event (AE) is defined as any untoward medical occurrence in a patient or clinical investigation subject administered a pharmaceutical product and that does not necessarily have to have a causal relationship with this treatment. An AE can therefore be any unfavorable and unintended sign (including an abnormal laboratory finding), symptom, or disease temporally associated with the use of erlotinib whether or not considered related to erlotinib.

During clinical trials, adverse events can be spontaneously reported or elicited during open-ended questioning, examination, or evaluation of a subject. (In order to prevent reporting bias, subjects should not be questioned regarding the specific occurrence of one or more adverse events.)

Adverse events (AEs) will be recorded in the case report form for the duration of the trial, regardless of whether or not the event(s) are considered related to trial medication. All AEs considered related to trial medication will be followed until resolution even if this occurs post-trial.

Adverse events (AEs) will use the descriptions and grading scales found in the revised Common Terminology Criteria for Adverse Events (CTCAE) version 4.0 (Appendix C). A list of adverse events that have occurred or might occur (Reported Adverse Events and Potential Risks) can be found in Section 6 (Pharmaceutical Information). The reported procedures to be followed are presented in the investigators' brochures.

In the context of multicenter clinical trials, Adverse Events can be characterized as either internal adverse events or external adverse events. From the perspective of one particular institution engaged in a multicenter clinical trial, internal adverse events are those adverse events experienced by subjects enrolled by the investigator(s) at that institution,

whereas external adverse events are those adverse events experienced by subjects enrolled by investigators at other institutions engaged in the clinical trial. In the context of a single-center clinical trial, all Adverse Events would be considered internal adverse events.

Unanticipated Problem

Any event, deviation, or problem that meets ALL of the following criteria:

- unexpected; AND
- possibly, probably or definitely related to study participation; AND fatal, life-threatening, or serious OR suggests greater risk of harm to study
- participant(s) or others than was previously known or recognized.

Unexpected

An event can be categorized as unexpected if it occurs in one or more subjects participating in a research protocol; and the nature, severity, or frequency of which is not consistent with either:

- i. The known or foreseeable risk of adverse events associated with the procedures involved in the research that are described in protocol-related documents such as: the IRB-approved research protocol; any applicable investigator brochure; the current IRB-approved informed consent document; or other relevant sources of information, such as product labeling and package inserts; or
- ii. The expected natural progression of any underlying disease, disorder, or condition of the subject(s) experiencing the adverse event and the subject's predisposing risk factor profile for the adverse event.

Serious Adverse Event (SAE)

An adverse event or suspected adverse reaction is considered "serious" if, in the view of either the investigator or sponsor, it results in any of the following outcomes:

- i. death,
- ii. a life-threatening adverse reaction,
- iii. inpatient hospitalization or prolongation of existing hospitalization,
- iv. persistent or significant incapacity or substantial disruption of the ability to conduct normal life functions, or
- v. a congenital anomaly/birth defect.

Important medical events that may not result in death, be life-threatening, or require hospitalization may be considered serious when, based upon appropriate medical judgment, they may jeopardize the patient or subject and may require medical or surgical intervention to prevent one of the outcomes listed above.

12.2 Determination of reporting requirements

Reportable Events

Any event that meets the definition of an Unanticipated Problem must be reported to the IRB within 5 business days. For multicenter studies, this would include such events that occur at external sites.

Other events that must be reported to the IRB include:

- The death of a participant in a “greater-than-minimal-risk” protocol being conducted at a site under the jurisdiction of the Einstein IRB, even if “anticipated”, if it occurs within 30 days of a study-related procedure or the administration of a study drug.
- A Protocol Deviation that may place the participant or others at greater medical, physiological, social risk or economic risk than was previously known or recognized.
- Any deviation from IRB or Institutional Policy or Procedure which has the potential to adversely impact one or more subject or the overall integrity of data collected.
- Any reporting the PI is required to report directly to the FDA (e.g. the PI is the sponsor- Investigator, a protocol involving the use of an HUD).
- Any incident, experience, or outcome that indicates that the participant or others were placed at greater medical, physiological, social risk or economic risk than was previously known or recognized.
- Any reporting that the IRB cites as a condition of approval of the protocol.
- Complaint from a participant or other individual when the complaint indicates unexpected risks or the complaint cannot be resolved by the research team.
- Deviation from the IRB Informed Consent Policy.
- Systematic data collection errors.
- Breach of confidentiality.
- Any action taken to eliminate an apparent immediate hazard to a research subject.
- Incarceration of a research subject.
- Sponsor or regulatory audit that requires corrective action.
- Suspension or restriction of an Investigator’s clinical professional license.
- Disqualification or suspension of the Investigator by the FDA, NIH or other agency.

A record of non-reportable events and deviations must be maintained by the PI in a log and for greater than minimal risk studies must be submitted to the IRB as part of the annual review of the protocol. Adverse events (AEs) will be recorded in the case report form for the duration of the trial, regardless of whether or not the event(s) are considered related to trial medication. All AEs considered related to trial medication will be followed until resolution even if this occurs post-trial.

Reporting requirements may include the following considerations:

- 1) whether the patient has received an investigational or commercial agent;
- 2) the characteristics of the adverse event including the grade (severity), the relationship to the study therapy (attribution), and the prior experience (expectedness) of the adverse event
- 3) the phase (1, 2, or 3) of the trial
- 4) whether or not hospitalization or prolongation of hospitalization was associated with the event.

An investigational agent is a protocol drug administered under an Investigational New Drug Application (IND) (5-AZA). In some instances, the investigational agent may be

available commercially, but is actually being tested for indications not included in the approved package label.

Steps to determine if an adverse event is to be reported in an expedited manner:

Step 1: *Identify the type of event using the NCI Common Terminology Criteria for Adverse Events (CTCAE) Version 4.0.* The CTCAE provides descriptive terminology and a grading scale for each adverse event listed.

Step 2: *Grade the event using the NCI CTCAE.*

Step 3: *Determine whether the adverse event is related to the protocol therapy (investigational or commercial).* Attribution categories are as follows: Unrelated, Unlikely, Possible, Probable, and Definite.

Step 4: *Determine the prior experience of the adverse event.* *Expected* events are those that have been previously identified as resulting from administration of the agent. An adverse event is considered *unexpected*, for expedited reporting purposes only, when either the type of event or the severity of the event is **NOT** listed in section 6.5. the current NCI Agent-Specific Adverse Event List for the investigational agent.

Step 5: *Review the "Additional instructions, requirements, and exceptions for this protocolspecific requirements for expedited reporting of specific adverse events that require specialmonitoring.*

Step 6: *Determine if the protocol treatment given prior to the adverse event included investigational agent(s), a commercial agent(s), or a combination of investigational and commercial agents.*

NOTE: If the patient received at least one dose of investigational agent, follow the guidelines for investigation agents. If no investigational agent was administered, follow the guidelines for non-investigational agents.

12.3 Reporting methods

Any event that meets the definition of an Unanticipated Problem must be reported to the Montefiore-Einstein IRB within 5 business days. The Unanticipated Problem Report Form can be found on the Einstein IRB website: <http://einstein.yu.edu/administration/institutional-review-board/forms.aspx>. All Reportable Events must be submitted to the IRB within 5 business days of the identification of the event by the research staff. Only the Principal Investigator may sign off on reportable event submissions, although any member of the research team may initiate the report. A record of non-reportable events and deviations must be maintained

by the PI in a log and for greater than minimal risk studies must be submitted to the IRB as part of the annual review of the protocol.

For events that are deemed reportable at participating sites, a copy of the reportable event must be submitted to Montefiore Medical Center within 2 business days. You may send to the Principal Investigator and the Study Coordinator. All contact information is located at the cover page of this document. If not reportable, Adverse Events should be logged in the CRF page, and any non-reportable serious and/or unanticipated adverse events should be logged on the Adverse Event Log provided by Montefiore for review at the Montefiore Data Safety Monitoring Committee meetings and during IRB annual review.

Montefiore will submit all reportable events to Astellas Drug Safety within 5 business days by submitting to: Astellas Drug Safety: [contact] OR [contact].

12.4 Trial Monitoring

This trial will be monitored by the Albert Einstein Cancer Center Data Safety Monitoring Committee (AECC DSMC). A copy of the monitoring plan is maintained at the CPDMU. The DSMC as part of its function performs quarterly reviews of Clinical Trials Compliance Audits, monthly reviews Adverse Events Reports, and monthly reviews of internally monitored Phase I/Phase II trials for accrual and response. Other monitoring activities are established as necessary in a protocol specific manner.

This trial will be part of the monthly Quality Assurance Audits. Each patient will be evaluated within 8 weeks of registration. This permits evaluation of consent, eligibility, and treatment/dose modification/Adverse Event (AE) reporting, and data quality for the first cycle (or month) of treatment. Patients at participating sites are evaluated for eligibility and consent at the time of registration by clinical and administrative staff.

This trial may also be eligible for quarterly Quality Enhancement Audit. Each audit consists of a review of regulatory documents, pharmacy drug accountability (if applicable) and patient case review, confirming eligibility, protocol compliance and source documentation

The results of the audit will be presented at the following month's DSMC meeting. The DSMC has the authority to close trial to patient accrual should the risk to patients be excessive or results require a corrective plan from the Principal Investigator. All study suspensions and closures will be forwarded to the IRB and study sponsor. All audit reports are forwarded to the DSMC and presented to the DSMC by the Audit Committee Coordinator.

12.5 Expedited reporting for investigational agents

Follow guidelines in section 12.2 regarding criteria that required expedited reporting.

For any adverse events that occur more than 30 days after the last dose of treatment, only those that have an attribution of possibly, probably, or definitely AND meet the reporting requirements in Sections 12.2 must be reported on an expedited adverse event report form as per guidelines in section 12.2

Adverse events that require expedited reporting are outlined below: for the investigational agent erlotinib.

The following be reported as a SAE:

- **Grade 2 (moderate) and Grade 3 (severe) Events** – Only events that are Unexpected AND Possibly, Probably or Definitely Related/Associated with the Intervention.
- **ALL Grade 4 (life threatening or disabling) Events** – Unless expected AND specifically listed in protocol as not requiring reporting.
- **ALL Grade 5 (fatal) Events** – When participant is enrolled and actively participating in the trial OR when event occurs within 30 days of the last study intervention.

Additional instructions, requirements and exceptions for this protocol::

With respect to determining the specific day by which the event must be reported, the day the reporter learns of the adverse event constitutes “Day 0”.

12.6 Responsibilities of participating sites

Serious adverse events will be reported to each participating institution according to protocol guidelines and local policies and procedures governing the local Institutional Review Board.

A copy of all SAE’s should be faxed to the Coordinating Center, Montefiore Medical Center (see cover page) within two (2) business days by the participating site. Other events that should be reported include: (1) any pregnancy occurring in association with use of erlotinib, and (2) any new information regarding any SAE.

12.7 Responsibilities of the Coordinating Center (Montefiore Medical Center) and Astellas.

The Coordinating Center (Montefiore Medical Center) will maintain records and

provide reports to Astellas for the following Adverse Experiences: (1) all serious, unexpected, adverse events, (2) any significant increase in the frequency of serious expected adverse events, and (3) an annual progress report including number of patients accrued, date on study, date off study, vital status (alive/dead and date alive/dead).

13.0 REMOVAL OF PATIENTS FROM PROTOCOL THERAPY:

Extraordinary medical circumstances or withdrawal of consent by the patient:

If, at any time, the constraints of this protocol are detrimental to the patient's health, and/or the patient no longer wishes to continue protocol therapy, the patient shall be withdrawn from protocol therapy. Patients will also be withdrawn from study for the following reasons:

1. **Disease Progression: Any patient with disease progression should be removed from study. Details and tumor measurements should be documented on flow sheets.**
2. Patient is unable to tolerate the toxicity resulting from the study treatment, even with optimal supportive care, in the opinion of the Treating Physician. Adverse event(s) that, in the judgment of the investigator, may cause severe or permanent harm or which rule out continuation of study drug.
3. The physician feels it is in the best interest of the patient to stop the treatment.
4. Inter current illness that would, in the judgment of the Investigator, affect assessment of clinical status to a significant degree or require discontinuation of study treatment
5. Non protocol chemotherapy or immunotherapy is administered during the study
6. Noncompliance with protocol or treatment—major violation
7. Suspected Pregnancy
8. Patient is lost to follow-up
9. Patient refuses to continue treatment (patient will continue to be followed for disease-free survival and overall survival)
10. Death

In this event notify:

Study PI (contact information on cover page of protocol)

Study Coordinator(contact information on cover page of protocol)

Regulatory Coordinator(contact information on cover page of protocol)

Clinical Trials Office: [contact] AND e-mail:

[contact]

***Document the reason(s) for withdrawal on flow sheets. Follow the patient for survival with follow-up forms as dictated by the protocol**

14.0 FOLLOW-UP:

Subjects who undergo surgery will have a post-surgery follow-up visit 30 days (± 3 days) after surgery. Subjects who do not receive surgery will have an end of treatment visit 30 days (± 3 days) after Post-Treatment Visit.

Any adverse event occurred during the study treatment should be monitored by subsequent follow-up visits until resolves to grade 1 or less, or until a new therapy is started.

Subjects who discontinue treatment for any reason, will be followed for survival. In addition off study evaluations will be done when treatment is discontinued -Section 7.0.

15.0 REGULATORY CONSIDERATIONS:

15.1 Protection of Human Subjects

The Investigator must ensure that patients or their legally acceptable representatives are clearly and fully informed about the purpose, potential risks and other critical issues regarding clinical trials in which they volunteer to participate. Preparation of the consent form is the responsibility of the Investigator and must include all elements required by CFR 21 Part 50.25 and the local IRB.

15.2 Compliance with the Protocol and Protocol Revisions

The study must be conducted as described in this approved protocol. The participating sites should not make any changes or revision to the protocol.

Any changes or revisions to the protocol must be provided to [name], Montefiore Medical Center and Astellas. The Investigator should not implement any deviation or change to the protocol without prior review and documented approval/favorable opinion from the IRB/IEC of an Amendment, except where necessary to eliminate an immediate hazard(s) to study patients.

Documentation of approval signed by the chairperson or designee of the IRB(s)/IEC(s) must be sent to Astellas. If the revision is an Administrative Letter, Investigators must inform their IRB(s)/IEC(s).

The Investigator must ensure that patients or their legally acceptable representatives are clearly and fully informed about the purpose, potential risks and other critical issues regarding clinical trials in which they volunteer to participate. Preparation of the consent form is the responsibility of the Investigator and must include all elements required by CFR 21 Part 50.25 and the local IRB.

16.0 DATA MONITORING / QUALITY ASSURANCE/ RECORD RETENTION:

Investigator responsibilities are set out in the ICH guideline for Good Clinical Practice (GCP) and in the US Code of Federal Regulations.

The Montefiore Medical Center, as coordinator of this study, is responsible for ensuring proper conduct of the study with regard to protocol adherence and the validity of the data recorded on the case report forms. The Principle Investigator ([name].) will monitor this study. The case report forms will be monitored every 3 months against submitted support documents for accuracy, completeness, adherence to the protocol and regulatory compliance.

U.S. FDA regulations (21CFR312.62[c] require all records and documents pertaining to the conduct of this study and the distribution of investigational drug, including CRFs, consents forms, laboratory test results and medication inventory records, must be retained by the Principal Investigator for 2 years after marketing application approval. If no application is filed, these records must be kept 2 years after the investigation is discontinued and the FDA and the applicable local health authorities are notified. Astellas will notify the Principle Investigator if an application is filed.

17.0 DATA SAFETY AND MONITORING BOARDS:

All trials initiated by the Montefiore Medical Center are subject to oversight by the Data Safety Monitoring Board (DSMB). This board meets once a month with any additional meetings scheduled when needed. The responsibilities are as follows:

- Familiarize themselves with the research protocol (s)
- Review interim analyses of outcome data and cumulative toxicity data summaries to determine whether the trial should continue as originally designed, should be changed, or should be terminated based on these data.
- The DSMB reviews trial performance information such as accrual information.
- The DSMB also determines whether and to whom outcome results should be released prior to the reporting of study results.
- All adverse events are reviewed by the committee with assurances that these have been in fact sent for review to all pertinent IRBs.
- Review of reports of related studies to determine whether the monitored study needs to be changed or terminated.
- Review major proposed modifications to the study prior to their implementation (e.g., termination, dropping an arm based on toxicity results or other reported trial outcomes, increasing target sample size).

Following each DSMB meeting, provide the study leadership with written information concerning findings for the trial as a whole related to cumulative toxicities observed and any relevant recommendations related to continuing, changing, or terminating the trial. The study leadership will provide information on cumulative toxicities and relevant recommendations to the local principal investigators to be shared with their IRB's.

18.0 STATISTICAL CONSIDERATIONS:

18.1 Study Design/Analytic Plan

- The primary statistical objectives of this single arm open label phase II study to obtain preliminary estimates of the rate of mediastinal nodal clearance and the rate of complete pathological response in patients with stage III NSCLC with EGFR mutations who received neoadjuvant erlotinib and had surgical resection. Historical data from the neoadjuvant studies with chemotherapy or chemoradiotherapy in resectable NSCLC patients had mediastinal nodal clearance between 15-40%. We hypothesize that patients with stage III EGFR mutated NSCLC treated with neoadjuvant erlotinib therapy must have comparable rates of mediastinal down staging and complete path response for this strategy to evaluate further in this subset of NSCLC patients.
- The mediastinal nodal clearance is defined as pathologically negative N2 disease in the final surgical resection specimen or mediastinoscopy. This can be objectively measured and has been confirmed as the best predictor of long term survival in patients with stage III NSCLC treated with neoadjuvant therapy and had surgical resection.
- Secondary objectives are to estimate objective overall response rate [ORR, i.e., complete response (CR) + partial response (PR)], disease control rate (CR+PR+SD), the surgical resection rate, the progression free (PFS) and overall survival (OS), and the safety of neoadjuvant erlotinib followed by surgical resection in patients with stage III EGFR mutated NSCLC.
- PFS is defined as the time from randomization until documented tumor progression or death from any cause. PFS is censored at the date of the last follow-up visit for patients who are still alive and who have not progressed. OS is defined as the time from the date of randomization to date of death due to any cause.
- Response rates will be summarized by computing proportions and corresponding 95% confidence intervals. Time to event endpoints will be analyzed using standard survival analytic methods, including the Kaplan-Meier approach for estimating the survival distributions. Median time to event and 95% confidence intervals will be estimated from the Kaplan-Meier curves. All primary and secondary analyses will be based on the intent-to-treat principle.

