1.1 Primary Objective

- To estimate the rate of mediastinal nodal clearance and complete pathological response after neoadjuvant erlotinib in patients with EGFR mutated stage III NSCLC.

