18.2 Sample Size/Accrual Rate

- Our study patient population comprise of the patients with stage III NSCLC who have activating EGFR mutation.
- Based on historical data, the mediastinal nodal clearance rate of 30% or higher will justify the further study of neoadjuvant erlotinib and the rate of 15% or less will be considered ineffective.
- An optimal two-stage phase II study⁴⁰ is designed to test the null hypothesis that the rate is 15% or less versus the alternative hypothesis that the response rate is at least 30%.
- The total sample size if the study will be 55 patients
- Nineteen (19) patients will be accrued in the first stage of phase II. **If 3 or fewer responses are observed during the first stage then the treatment will be concluded early for lack of efficacy.** Otherwise, 36 additional patients will be accrued for the second stage. **If 12 or fewer responses among 55 patients are observed by the end of this phase II study, no further investigation of this treatment regimen is warranted.**
- The power under this design is 80% and the type I error is 0.05. The probability of early stopping at the first stage is 68.4% if the true response rate is 15%. If the true response rate is 30%, the probability of early stopping at the first stage is 13.3%.
- By the end of this study, response rate will be estimated and its exact 95% confidence interval will be calculated. A total of 55 patients ensure that the 95% confidence interval for the estimated response rate will be within +/- 15.7%.
- The Montefiore Medical Center will initiate the study. Additional 4-5 sites will be subcontracted by Montefiore Medical Center to expedite accrual in the study.
- With the initial anticipated accrual of 1-2 patients per month across 4-5 centers, it will take approximately 12 months for the first stage of the study. The total accrual period is assumed to be approximately 24-36 months, with a follow-up period of an additional 12 months after the last patient is enrolled.

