18.3 Randomization and Stratification

This will be a single arm phase II study and no randomization or stratifications will be involved

18.4 Evaluation of toxicity.

All patients will be evaluated for toxicity from the time of their first treatment with erlotinib. All of the surgical procedures in the protocol are the usual standard of care in treating patients with stage III NSCLC. However, we will monitor and record all postoperative complications. Certain postoperative complications are expected after lung resection and/or mediastinoscopy. We will particularly monitor 30 day mortality, development of bronchopulmonary fistula or prolonged wound healing. If the rate of these is more than what is expected as standard of care, the regulatory authorities will be reported and the trial will be suspended for toxicity.

18.5 Evaluation of response.

All patients who meet the eligibility criteria and have received at least one dose of treatment will be assessed for response to treatment.

19.0 REFERENCES:

5. Non-small Cell Lung Cancer Collaborative Group. 1995. Chemotherapy in non-small cell lung cancer: a meta-analysis using updated data on individual patients from 52 randomized clinical trials. *Br Med J* 311(7010):899-909.

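### Section 18.1 words the primary rates as if only resected patients count, against its own intent-to-treat sentence, its endpoint definition, 1.1 and 18.2; and it does not say whether an EUS/EBUS-only negative is clearance

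*Combined protocol and SAP*

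**What the plan says.** Statements on who is in the primary rate:

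- **18.1, primary objective sentence:** both rates are for "patients with stage III NSCLC with EGFR mutations who received neoadjuvant erlotinib and had surgical resection".
- **18.1, last bullet:** "All primary and secondary analyses will be based on the intent-to-treat principle".
- **18.1, endpoint definition:** clearance is "defined as pathologically negative N2 disease in the final surgical resection specimen or mediastinoscopy". A patient with no resection specimen can therefore be a responder.
- **1.1:** "To estimate the rate of mediastinal nodal clearance and complete pathological response after neoadjuvant erlotinib in patients with EGFR mutated stage III NSCLC". There is no resection condition.
- **18.2:** "Nineteen (19) patients will be accrued in the first stage of phase II", and the final rule is "If 12 or fewer responses among 55 patients are observed by the end of this phase II study". The precision statement uses the same number: "A total of 55 patients ensure that the 95% confidence interval for the estimated response rate will be within +/- 15.7" points.

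Statements on how clearance is shown:

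- **4.2:** non-progressing patients who do not go to surgery are restaged by EUS/EBUS or by mediastinoscopy. The 6.1 calendar makes this restaging a requirement.
- **6.1, footnote g:** EUS or EBUS may stand in for mediastinoscopy where clinically appropriate, but the footnote opens by speaking of documenting N2 disease.
- **18.1:** the clearance definition does not name EUS or EBUS.

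No section says how to score a patient who has no mediastinal pathology after treatment.

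**The concern.** The resected patients are an outcome-dependent subset. Section 3.1 admits unresectable patients. Section 4.1 takes patients who progress, or who are not surgical candidates, off study before surgery. The resection rate is itself a secondary endpoint. A clearance rate computed only in resected patients therefore leaves out many of those for whom treatment did not work, and it is not the quantity that the 15% and 30% benchmarks test in 18.2. A trial that fails its own rule could report a primary rate at or above the 30% target, with an interval based on fewer than 55 patients.

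The EUS/EBUS gap is a separate matter. It affects the response count that enters the go/no-go rule, because two careful readers could score the same unresected patient differently.

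**Working it through.** **1. The plan's design figures.** Inputs from 18.2: stage 1 stops at 3 or fewer of 19; the final no-go is 12 or fewer of 55; null rate 15%, target rate 30%.

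- P(early stop) = P(X1 ≤ 3), with X1 ~ Bin(19, p).
- P(go) = sum over x1 = 4 to 19 of P(X1 = x1) × P(X2 > 12 − x1), with X2 ~ Bin(36, p).

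| True rate p | P(early stop) | P(go) |
|---|---|---|
| 0.15 | 0.684 | 0.0477 |
| 0.30 | 0.133 | 0.8006 |

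These match the stated 68.4%, 13.3%, type I error 0.05 and power 80%. The rule is sound when the denominators are accrued patients.

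**2. The literal 18.1 denominator.** Take the largest no-go result, 12 of 55, and suppose all 12 clearances were in resected patients. The documents assume no resection rate for this trial. The background gives 50% for the surgical arm of another trial, so the resected numbers below are assumptions. Intervals are exact (Clopper-Pearson).

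| Denominator | Rate | 95% CI |
|---|---|---|
| 55 accrued | 12/55 = 21.8% | 11.8 to 35.0 |
| 40 resected | 12/40 = 30.0% | 16.6 to 46.5 |
| 28 resected (28/55 = 51%) | 12/28 = 42.9% | 24.5 to 62.8 |

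With 41 resected the rate is 12/41 = 29.3%, so with 41 or more it stays below 30%. Not all 12 need to be resected for the effect: with 28 resected, 9/28 = 32.1% (15.9 to 52.4) already exceeds 30%, while 8/28 = 28.6% does not.

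**3. The stated precision.** There are two ways to read the ±15.7 points, each taken at its worst over all possible outcomes.

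| n | Longest arm of exact CI | Half-width of exact CI |
|---|---|---|
| 55 | 14.1 | 13.8 |
| 45 | 15.68 | 15.3 |
| 44 | 15.87 | 15.4 |
| 43 | 16.1 | 15.62 |
| 42 | 16.3 | 15.81 |
| 28 | 20.2 | 19.4 |

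The promise holds at 55. It fails only at 44 or fewer patients by the longest arm, or at 42 or fewer by half-width.

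**4. EUS/EBUS-only negatives.** Suppose the true clearance rate is 30% and a share s of clearances is shown only by EUS/EBUS and not counted. The scored rate is 0.30 × (1 − s), which goes into the formula in step 1. The shares are assumptions.

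| s | Scored rate | P(go) |
|---|---|---|
| 0 | 0.30 | 0.80 |
| 0.10 | 0.27 | 0.67 |
| 0.20 | 0.24 | 0.49 |

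**The case against.** The strongest reply is that one phrase stands against several operative statements. The intent-to-treat sentence covers every primary and secondary analysis. Section 18.2 ties the reported estimate and its exact interval, as well as the decision rule, to 55 patients. Reporting 12/28 as the primary rate would breach that text. The phrase also has innocent readings: it may describe the regimen, or it may reflect that complete pathological response needs a resected specimen. This largely stands, and it is why intent-to-treat is the better-supported reading. But nothing ranks those statements above the sentence that defines the primary rates, and that sentence covers clearance as well as pathological response.

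On EUS/EBUS, footnote g applies to a calendar row that includes the post-treatment visit, and its substitution sentence is not limited to baseline. Counting an EUS/EBUS negative is therefore a reasonable reading. It is still not in the endpoint definition.

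Three stronger inferences are tempting, and the documents do not support them:

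- **That the go/no-go rule is faulty.** It reproduces exactly on accrued patients.
- **That 18.5 sets a rival primary population.** It says "All patients who meet the eligibility criteria and have received at least one dose of treatment will be assessed for response to treatment". That describes who is assessed and sets no denominator for clearance. It may mean RECIST response, the subject of section 7, although 18.2 does use the word responses for clearance.
- **That the ±15.7 precision necessarily fails.** It fails only below the resected numbers in step 3, and the plan gives no expected number.

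**Conclusion.** The inconsistency is real and should be corrected. Read literally, 18.1 gives a primary rate in a subset selected for success, against its own intent-to-treat sentence, its endpoint definition, 1.1 and 18.2. The design is not in question.

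The size depends on how many patients are resected, which the documents do not give. A no-go 12/55 could be shown as 30.0% at 40 resected or 42.9% at 28, if all clearances fell in resected patients. At 41 or more resected it could not reach 30%.

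The unresolved EUS/EBUS scoring can move the decision itself. At a true 30%, P(go) drops from 80% to 67% or 49% if one in ten or one in five clearances goes uncounted. Those shares are illustrative. The textual mismatches are certain; the consequences are conditional on these assumptions.

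**What to change.** 1. In 18.1, delete the surgical-resection condition from the primary-rate sentence.
2. State in 18.1 and 18.2 that the primary clearance rate, its interval and both Simon stages use the accrued intent-to-treat patients.
3. Count patients without documented pathological nodal clearance (progression, withdrawal, no restaging) as not cleared, and unresected patients as not achieving complete pathological response.
4. Report resected-only rates as labelled descriptive secondaries.
5. Before the stage 1 decision, reconcile the 18.1 definition with 4.2 and footnote g of 6.1 by stating whether an EUS/EBUS-only negative counts as clearance. Run the opposite scoring as a sensitivity analysis.
6. Optionally, clarify that 18.5 describes who is assessed. The handling of ineligible or never-dosed patients is a matter of convention and can be left to the sponsor.

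**Cost:** wording only. There are no extra patients or procedures, and the design stays 3/19, 12/55. The reported rate will be lower than a resected-only rate. The EUS/EBUS choice costs something either way: not counting such negatives lowers P(go) as shown, and counting them accepts needle sampling as proof of clearance.
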